## 7.2. Participant Discontinuation/Withdrawal from the Study

Participants will be discontinued (withdrawn) from the study in the following circumstances:

- enrollment in any other clinical study involving an investigational product or enrollment in any other type of medical research judged not to be scientifically or medically compatible with this study

- participation in the study needs to be stopped for medical, safety, regulatory, or other reasons consistent with applicable laws, regulations, and good clinical practice (GCP)
- investigator decision
  - the investigator decides that the participant should be discontinued from the study
- subject decision
  - the participant requests to be withdrawn from the study
- Legal guardian decision
  - the legal guardian requests the participant to be withdrawn from the study

Participants discontinuing from the study prematurely for any reason should have AE and other safety follow-up specified for the ETV. See Section 1.3 (Schedule of Activities), Section 8.2 (Safety Assessments), and Section 8.3 (Adverse Events and Serious Adverse Events).

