### 5.1.3 Definition of Study Period Time Interval

**Table AMAM.5.1** displays a list of study periods along with the definition of which participants will be considered to have entered the study period and when the individuals start and end the study period. The table shows both a date and a time.

To calculate the length of any time interval or time period in this study the following formula will be used:

$$\text{Length of interval (days)} = \text{End Date} - \text{Interval Start Date} + 1$$

To convert any time length from days to years, the following formula will be used:

$$\text{Length of interval (years)} = \text{Length of interval (days)} / 365.25$$

To convert any time length from days to weeks, the following formula will be used:

$$\text{Length of interval (weeks)} = \text{Length of interval (days)} / 7$$

Only for the purpose of calculating the length of study period time intervals, the words “prior to” in **Table AMAM.5.1** should be understood to mean “the day before” while the words “after” should be understood to mean “the day after.” For the purpose of determining whether a date/time lies within an interval these words are intended to convey whether the start or end of the period is inclusive of the specified date.

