**Table AMAM.5.1. Study Period Definitions**

Study Period	Interval Start Definition	Interval End Definition
Screening	Informed consent date	Prior to the start of Period 1.
Period 1	At the date/time a of first dose of study intervention. For participants who are assigned treatment but not dosed, Period 1 starts on the date of treatment assignment.	Prior to the start of Period 2. For participants who discontinue before or on the Week 12 visit, Period 1 ends at the latest date of 1) study intervention discontinued date or 2) last study intervention visit date.
Period 2	At the Week 12 dosing date/time a . If the participant is unable to be dosed at the Week 12 visit, the Period 2 starts at the Week 12 Visit. If the participant misses the Week 12 visit, the Period 2 starts at Day 91.	After the Week 52 visit date. For participants who discontinue prior to Week 52, Period 2 ends at the latest date of 1) study intervention disposition date or 2) last study intervention visit date.
Study Treatment Period	Same as Period 1 interval start	The latest of the following dates: (1) the end of the Period 1, (2) the end of the Period 2.

Follow-up Period	All participants who had Visit 801 or Visit 802 are considered to have entered the Follow-up Period. The latest of Period 1 or Period 2 interval end date.	The last date of the last study visit and study disposition date.
-------------------------	------------------------------------------------------------------------------------------------------------------------------------------------------------	-------------------------------------------------------------------

a Missing dose time will be imputed as the earliest time that is consistent with available data about dose time. For example, suppose the minutes are missing but hour is present. In this case, we would impute the minutes to be 0.

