## 5.6.2 Adverse Events

A treatment-emergent adverse event (TEAE) is defined as an event that first occurred or worsened in severity after baseline. The Medical Dictionary for Regulatory Activities (MedDRA) Lowest level Term (LLT) will be used in the treatment-emergent computation. The maximum severity for each LLT during the baseline period will be used as baseline. For events with a missing severity during the baseline period, it will be treated as “mild” in severity for determining treatment-emergence. Events with a missing severity during the postbaseline period will be treated as “severe” and treatment-emergence will be determined by comparing to baseline severity. For events occurring on the day of first taking study medication, the start times of the study treatment and adverse event (AE) will be used to determine whether the event was pre-versus post-treatment. If the start time for the AE is missing, it will be assumed to have started in the postbaseline period.

The summary analyses will be presented for the safety population corresponding to the Study Treatment period alone and with the follow-up period as described in [Table AMAM.5.3](#). Summary tables include the number and percentage of participants reporting an event. For events that are sex-specific (as defined by MedDRA), the number of participants at risk will include only participants from the given sex.

[Table AMAM.5.3. Analysis of AEs](#)

Analysis
Overview of AEs
Summary of TEAE PTs by decreasing frequency
Summary of TEAE PTs by decreasing frequency within SOC
Summary of TEAE PTs by maximum severity by decreasing frequency
Listing of AEs leading to study treatment discontinuation
Listing of SAEs
Listing of Deaths

Abbreviations: AE = adverse event; PT = Preferred Term; SAE = serious adverse event; SOC = System Organ Class; TEAE = treatment-emergent adverse event.

For the Safety Population, the baseline period and postbaseline will be defined as follows:

- the baseline period is the Screening Period.
- the postbaseline period will be a) the Study Treatment Period alone, and b) the Study Treatment combined with the Follow-up Period.

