## 6.6 Appendix 6: Clinical Trial Registry Analyses

Additional analyses will be performed for the purpose of fulfilling the Clinical Trial Registry (CTR) requirements.

Analyses provided for the CTR requirements include the following:

Summary of AEs, provided as a dataset which will be converted to an XML file. Both SAEs and 'Other' AEs are summarized by study intervention group, by MedDRA PT.

- An AE is considered 'Serious' whether or not it is a TEAE.
- An AE is considered in the 'Other' category if it is both a TEAE and is not serious. For each SAE and 'Other' AE, for each term and study intervention group, the following are provided:
  - the number of participants at risk of an event
  - the number of participants who experienced each event term
  - the number of events experienced.
- Adverse event reporting is consistent with other document disclosures (e.g., the CSR, manuscripts, and so forth.

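### The Follow-up Period opens only to participants who attended V801 or V802, so a collected AE after treatment in someone with neither visit falls outside both AE windows.

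*SAP*

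**What the plan says.** SAP 5.1.3 introduces Table AMAM.5.1 as giving "the definition of which participants will be considered to have entered the study period and when the individuals start and end the study period". Its entries are therefore operative definitions. Four of them, with the AE section, matter here.

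- **Follow-up entry:** "All participants who had Visit 801 or Visit 802 are considered to have entered the Follow-up Period".
- **Follow-up end:** "The last date of the last study visit and study disposition date".
- **Treatment end, early stopper in Period 1:** "Period 1 ends at the latest date of 1) study intervention discontinued date or 2) last study intervention visit date".
- **Treatment end, early stopper in Period 2:** "Period 2 ends at the latest date of 1) study intervention disposition date or 2) last study intervention visit date". For a Week 52 completer, Period 2 closes with the Week 52 visit.
- **AE windows (SAP 5.6.2):** "the postbaseline period will be a) the Study Treatment Period alone, and b) the Study Treatment combined with the Follow-up Period".

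On visits, SAP 1.2 and Protocol 7.1 send participants who stop study drug early to an early termination visit (ETV) and then to post-treatment follow-up, which SAP 1.2 names as V801 and V802. Protocol 7.2, on leaving the study itself, says: "Participants discontinuing from the study prematurely for any reason should have AE and other safety follow-up specified for the ETV". It does not name V801 or V802. Protocol 8.3.2 releases investigators from actively seeking AEs only once the participant has discontinued or completed the study.

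**The concern.** Entry to a safety window depends on attending a later visit. A participant who dies, withdraws, is lost, or misses both visits never enters the Follow-up Period, even with recorded time in the study after treatment ended. The people left out are those who did not come back, and some may have stayed away because they were unwell.

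At stake are the tables described as covering treatment plus follow-up: the AE overview and the TEAE summaries by preferred term, by system organ class and by maximum severity. SAP 5.6 also lists safety data from follow-up, and SAP 5.7 lists Crohn's-related emergency visits, hospitalizations and surgeries over treatment plus follow-up. If follow-up there means the period defined in the table, those listings have the same gap.

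**Working it through.** The plan states no figure to reproduce. The check is to apply the rules to a case and then bound the size.

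**1. Rules applied to a hypothetical participant.** Assumed days, for illustration only: Study Treatment Period ends Day 60, a new AE starts Day 75, study disposition is Day 90.

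| | Window (a): treatment alone | Window (b): treatment plus follow-up |
|---|---|---|
| V801 or V802 attended | out (75 > 60) | in (60 < 75 ≤ 90) |
| Neither attended | out | out (Follow-up never entered) |
| Entry rule changed as proposed below | out | in |

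The AE and its date are the same in every row. Between the first two rows, only attendance differs.

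**2. Who can be in the second row.** Anyone not entering AMAZ whose study participation runs past the Study Treatment Period: an early stopper, or a Week 52 completer who declines or is ineligible for AMAZ and has neither visit.

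**3. Length of the exposed interval.** It runs from the end of the Study Treatment Period to study disposition.
- It is zero when the two dates coincide.
- The SAP does not say whether the ETV is a study intervention visit. If it is, the interval starts after the ETV.
- The ceiling is the whole follow-up allowance. Protocol 1.1 gives a 73-week maximum, up to 5 weeks of screening, 12 of induction and 40 of maintenance: 73 − 5 − 12 − 40 = 16 weeks.

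**4. Weight of one event.** SAP 3 gives 6 enrolled participants: 1/6 = 16.7 percentage points, for example a preferred term shown as 0/6 instead of 1/6.

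**5. Outputs that still show the event.**
- Deaths are listed from screening to the end of participation for all entered participants (SAP 5.6.2.1).
- The SAE listing has no stated window (SAP 5.6.2.1).
- Registry SAEs count whether or not they are treatment-emergent (SAP 6.6).
- The AESI listing is no backstop, because by default it covers the Study Treatment Period only (SAP 5.6.7).
- Table AMAM.5.3 has no listing of all AEs, so a non-serious event depends on the TEAE tables or on the follow-up listing.

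**The case against.** The strongest reply is that the path is narrow and the plan handles most of what matters on it. Much of that stands, and it rules out four stronger conclusions that a reader might draw.

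- **That the gap is routine for early stoppers.** Those who stop drug are required to have post-treatment visits. Protocol 7.2 concerns leaving the study; if drug and study end together, the two disposition dates may coincide and active AE collection ends, leaving little or no interval. Likewise, a death or loss that itself ends treatment may set the treatment end date and so fall in window (a).
- **That each affected participant loses 16 weeks, or 16/68 = 23.5% of the 68 weeks after first dose (73 − 5).** Sixteen weeks is the whole follow-up allowance. Someone who leaves before V801 loses less, and attending V801 alone opens the window. The full loss would need a participant who remains in the study throughout and attends neither visit.
- **That serious events disappear.** They drop out of the TEAE tables but remain in the listings and the registry count.
- **That registry non-serious AEs are certainly lost.** SAP 6.6 says "An AE is considered in the 'Other' category if it is both a TEAE and is not serious", but does not refer to the windows in SAP 5.6.2. The TEAE definition there requires onset or worsening after baseline and sets no upper limit. The loss follows only if the windows bound treatment-emergence.

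The compound level safety standards cited in the SAP are not part of these documents and might hold a rule. None of this removes the gap in the text: nothing in the protocol or SAP assigns the interval to a window when neither visit took place. Elsewhere the same table does plan for missed events, with a Day 91 start for Period 2 if the Week 12 visit is missed. Its follow-up end date also does not depend on V801 or V802.

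**Conclusion.** The point holds, as a small and conditional defect. As written, an AE collected after the Study Treatment Period in a participant with neither V801 nor V802 is in neither AE window. It is missing from the TEAE overview, preferred-term, system organ class and severity tables that include follow-up and, on one reading, from the follow-up listings in SAP 5.6 and 5.7. The clear loss is non-serious AEs and the TEAE tables.

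One omitted event changes an incidence by 16.7 points with six participants. The time at risk is between nil and 16 weeks per affected participant, and normally shorter than 16. This rests on reading the table as a definition, as SAP 5.1.3 describes it, and on no overriding rule in the compound level standards. Whether any of the six is in this position is unknown. It is still worth settling by rule, so that assignment of a late event does not have to be decided after the data are seen.

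**What to change.** Replace the entry rule in the Follow-up row of Table AMAM.5.1 with:

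> Every mITT participant who does not enter AMAZ and whose last study visit, death or study disposition date is later than the end of the Study Treatment Period enters the Follow-up Period on the day after the Study Treatment Period ends, whether or not V801 or V802 took place. The period ends on the latest of last study visit, death and study disposition date.

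The condition on a later date prevents a follow-up period that starts after it ends. Report attendance at V801 and V802 as a disposition count only. Window (a) is unchanged.

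The cost is one table row and one derivation line. The visit and disposition dates are already used in the table, and deaths are already to be listed, so no new data collection should be needed.

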- aa Visit procedures and assessments must be completed prior to dosing, except as noted in applicable footnotes above.
- ab With sponsor approval, CCI [REDACTED]  
[REDACTED]
- ac CCI [REDACTED].
- ad Visit 2 may be done over CCI [REDACTED].

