### **8.2.8. Clinical Laboratory Tests**

#### Visits and Times

The clinical laboratory tests listed in Appendix 10.2 will be conducted at the study visits specified in the SoA (Section 1.3).

Retesting is allowed during the screening period (see Section 5.4.1).

Additional clinical laboratory tests, including local tests, may be performed at any time during the study as determined necessary by the investigator for immediate participant management or safety or as required by local regulations.

Except where otherwise stated (for example, for postdosing PK sample), samples for laboratory tests should be collected prior to dosing.

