### 5.6.3 Clinical Laboratory Evaluations

As described fully in compound level safety standards and in the laboratory-related PhUSE white papers (PhUSE 2013, 2015), the clinical laboratory evaluations will be summarized with the following displays for the Safety Population during the Study Treatment period only as described in [Table AMAM.5.4](#).

[Table AMAM.5.4. Clinical Laboratory Analyses](#)

Analysis
Treatment-emergent abnormal high lab values (that is, participants shifting from a normal/low maximum baseline value to a high maximum postbaseline value) or low lab values (that is, participants shifting from normal/high minimum baseline value to a low minimum postbaseline value)
Scatter plot of maximum (minimum) postbaseline value versus maximum (minimum) baseline value
Shift tables showing the number of participants who shift from each category of maximum (minimum) baseline observation to each category of maximum (minimum) postbaseline observation. Here, categories may be low, normal, or high with cut-offs defined in the compound level safety standards.
Listing of abnormal findings

For these displays, the postbaseline periods will include the Study Treatment Period alone. Postbaseline measurement of continuous analysis (for example, boxplots) will include only scheduled measurements, while postbaseline categorical analysis (for example, shifts) will include both scheduled and unscheduled measurements.

Measurements are defined to be in the baseline periods as follows:

- Safety Population:
  - For analyses of continuous measurements: the last scheduled or unscheduled non-missing measurement recorded during the Screening Period.
  - For analyses of categorical measurements: all scheduled or unscheduled non-missing measurements recorded during the Screening Period.

For any lab given on the day of first taking study medication at the start of the postbaseline period, the start time of the study intervention will be used to determine whether the lab was pre- versus postbaseline. If time for the lab is missing, it will be assumed to be in the baseline period (that is, we assume the protocol defined order of procedures was followed).

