## 5.6.6 Immunogenicity

An individual sample is potentially examined multiple times in a hierarchical procedure to produce a sample anti-drug antibodies (ADA) assay result and potentially a sample neutralizing anti-drug antibodies (NAb) assay result. A participant has treatment-emergent anti-drug antibodies (TE ADA) when ADAs are induced or boosted by exposure to study drug (i.e., when at least 1 postbaseline ADA sample has a 4-fold increase in titers compared to baseline (if ADA were present at baseline) or has a titer 2-fold greater than the minimum required dilution of 1:10 (if no ADAs were present at baseline).

Compound level safety standards will be followed in the analyses of immunogenicity. Listings of immunogenicity assessments will be provided.

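### When the time of first dose is incomplete, the earliest-time rule can class a correctly drawn pre-dose laboratory sample as postbaseline

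*SAP*

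**What the plan says.** **Period boundary.** In SAP Table AMAM.5.1 the Screening period ends "Prior to the start of Period 1", and Period 1 starts at the date and time of first dose. Footnote a to that start time reads "Missing dose time will be imputed as the earliest time that is consistent with available data about dose time". Its only example has the hour known and the minutes missing: "In this case, we would impute the minutes to be 0".

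**Laboratory rule.** SAP 5.6.3 takes laboratory baseline from the Screening period. For a sample on the day of first dose, "the start time of the study intervention will be used to determine whether the lab was pre- versus postbaseline". If the sample time is missing, the sample is put in the baseline period, on the reasoning that "we assume the protocol defined order of procedures was followed". No matching provision covers a recorded sample time with a missing or partial dose time.

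**Protocol order.** The Schedule of Activities (Protocol 1.3, footnote aa) states "Visit procedures and assessments must be completed prior to dosing, except as noted in applicable footnotes above". Protocol 8.2.8 says that, apart from stated exceptions such as the post-dose PK sample, "samples for laboratory tests should be collected prior to dosing".

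**Adverse events.** SAP 5.6.2 treats an event on the first-dose day with no start time as postbaseline.

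**The concern.** An early imputed dose time suits adverse events: it errs toward treatment-emergent, as SAP 5.6.2 already does. For laboratory samples the order is fixed by protocol, and the SAP relies on that order when the sample time is missing. Moving the dose earlier can push a pre-dose sample across the boundary but can never bring one back. Which of the two clock times is incomplete then decides how the same blood draw is classed.

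A displaced Visit 2 value leaves the baseline maximum or minimum and enters the postbaseline one. Those extremes feed the treatment-emergent high and low counts, the shift tables and the scatter plots in SAP 5.6.3. The displaced value also stops being the last Screening value, which is the baseline for continuous analyses.

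**Working it through.** The plan states no figure that depends on this rule, so there is none to reproduce. The check applies the rules to test times.

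**Inputs**
- Imputation of a missing dose time: Table AMAM.5.1, footnote a.
- Sample before dose start is baseline, otherwise postbaseline; missing sample time is baseline: SAP 5.6.3.
- Number enrolled, 6: SAP Section 3.
- Assumed for illustration: true dose at 10:40, with all samples truly drawn before it.

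**Step 1. Classification**

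| Sample time | Correct class | Dose recorded as hour 10 only (imputed 10:00) | Dose time wholly missing, if read as 00:00 |
|---|---|---|---|
| 09:00 | baseline | baseline | postbaseline (wrong) |
| 09:50 | baseline | baseline | postbaseline (wrong) |
| 10:20 | baseline | postbaseline (wrong) | postbaseline (wrong) |
| missing | baseline | baseline | baseline |

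The third column follows from the SAP's own example. The fourth extends it: the SAP gives no value for a wholly missing time.

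**Step 2. How often, given an hour-only dose time.** Let the sample be drawn g minutes before the dose, and assume the dose minute is uniform over 0 to 59. The sample is misclassed when the dose minute is at least g, so the share is (60 − g)/60 for g up to 60, and 0 beyond:
- g = 5: 55/60 = 92%
- g = 15: 45/60 = 75%
- g = 30: 30/60 = 50%
- g = 45: 15/60 = 25%
- g = 60 or more: 0%

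These shares are conditional on an hour-only dose time. The documents give no rate for that.

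**Step 3. From misclassification to a false finding.** SAP 5.6.3 defines a treatment-emergent high as a normal or low maximum baseline followed by a high maximum postbaseline value, and mirrors this for lows. Baseline for categorical analyses is every scheduled and unscheduled Screening value. The displaced Visit 2 value must therefore be abnormal, and no earlier Screening value of that analyte may be abnormal in the same direction.

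If no later value is abnormal either, the participant has no abnormal result after dosing and the flag is plainly false. If a later value is abnormal, a real postbaseline abnormality exists whatever happens to the Visit 2 sample. By the letter of the definition the category still changes, because a correctly placed Visit 2 value would have made the baseline extreme abnormal. The point rests on the plainly false case.

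**Step 4. Size.** One such participant moves a proportion from 0/6 = 0% to 1/6 = 16.7%.

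**The case against.** **The trigger is remote.** Protocol 6.1 (Time of Doses) requires the actual time of every dose in the eCRF, Protocol 6.4 has site staff give every dose on site, and there are at most six first-dose times. This stands, and it sets the priority. The 16.7 points is also simply what any one event weighs among six people; it does not measure this rule. SAP 5.6.3 lists abnormal findings, so a flagged Visit 2 value could be caught by hand.

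**A rule may exist elsewhere.** SAP 5.6.3 refers to compound level safety standards that are not part of these documents. The phrase about available data could also be stretched to include the time of a pre-dose sample, although the SAP's example uses only the recorded part of the dose time. The Visit 2 laboratory schedule is not legible, but a rule for first-dose-day samples presupposes that they are taken. None of this removes the conflict in the SAP as written.

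**Stronger readings a reader might infer**
- *Abnormal values from active Crohn's disease would become treatment-emergent.* Participants must have active disease at screening (Protocol 5.1), so such an abnormality will often already be in an earlier Screening value. It then cannot count.
- *Pre-existing antidrug antibodies would read as treatment-emergent.* SAP 5.6.6 sets no first-dose-day timing rule. Its criterion "has a titer 2-fold greater than the minimum required dilution of 1:10 (if no ADAs were present at baseline" does not say that a missing baseline counts as no antibodies. Results are only listed.
- *Vital signs and PK are affected too.* SAP 5.6.4 provides vital signs as listings with no time-of-day rule, and the SAP specifies no PK analysis.

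**Conclusion.** The laboratory point holds and is minor. With a partial first-dose time and a recorded sample time, the stated rules class a correctly drawn pre-dose sample as postbaseline when it falls in the same clock hour as the dose. This conflicts with the protocol order and with the SAP's own treatment of a missing sample time.

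That every timed sample of the day would be displaced is only an inference. It requires a wholly missing dose time to be read as 00:00, which the SAP does not state.

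A false treatment-emergent finding further needs the abnormality pattern in Step 3. If that occurs, one participant adds 16.7 percentage points to a descriptive proportion. The conclusion assumes that laboratory samples are taken at Visit 2 and that the compound level standards contain no overriding rule. It does not extend to immunogenicity, vital signs or PK.

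**What to change.** Leave footnote a as it is. It defines the start of Periods 1 and 2 and works in the intended direction for adverse events; restricting it to adverse events would leave incomplete dose times undefined for every other use of those boundaries.

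Add one sentence to SAP 5.6.3 only:

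*If the time of first dose is missing or partial and the order cannot be determined, a scheduled Visit 2 laboratory sample collected on the day of first dose is treated as baseline, because the protocol requires it before dosing.*

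In the worked example, the 10:20 sample becomes baseline. With the dose hour recorded as 10, a sample timed at 11:05 would still be postbaseline, because the order is then known.

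The cost is one SAP sentence and one line of derivation code. A sample drawn after dosing in error, with no usable dose time, would stay in baseline; the SAP already accepts that risk for a missing sample time.
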